Anamorelin has potential favorable effects on bone. Pulsatile GH secretion declines with aging and this likely contributes to bone loss and fracture risk. GH stimulation could counter bone loss as it stimulates osteoblast proliferation and differentiation *in vitro* (30). The effect of anamorelin on bone turnover or other bone parameters has not been reported, but treatment with another ghrelin receptor agonist, MK-669, for 9 weeks significantly increased the bone formation markers, serum osteocalcin by 29% and bone-specific alkaline phosphatase by 10.4%, and it also increased urinary N-telopeptide by 22.6% in functionally impaired older adults (30).

Anamorelin may be more effective on muscle than exogenous GH or IGF-1. Anamorelin stimulates the release of GH in its normal pulsatile pattern. Pulsatile GH affects muscle through increases in circulating and intramuscular IGF-1 (31). Circulating IGF-1, which is largely of liver origin, stimulates muscle protein synthesis by binding to IGF-1 receptors on myocytes and activating the mTOR pathway (31). In addition to increasing circulating levels of IGF-1, GH binds to its receptors on myocytes to stimulate the production of intramuscular

IGF-1 which acts locally to inhibit myostatin and promote satellite cell (myocyte) activity (32). Exogenous nonpulsatile GH treatment increases lean mass (33) but its use is limited by side effects (edema, arthralgias, paresthesias) that have not been seen in the anamorelin trials. Exogenous recombinant human (rh) IGF-1, unlike anamorelin, has no impact on intramuscular IGF-1 production.

Objectives and endpoints

Our central hypothesis is that anamorelin will increase muscle mass. We will also assess the secondary and exploratory outcomes described below in OS adults. To test this hypothesis, we will conduct a double-blind, 2-armed, parallel-group intervention trial in men and postmenopausal women age 50 and older with OS. Participants will be randomly assigned in a one to one ratio to: anamorelin or placebo and treated for 12 mo.

Specific aims

1. Primary aim To determine and compare the effects of anamorelin vs placebo on muscle mass by D₃-creatine dilution in OS adults. *Hypothesis: Anamorelin will increase muscle mass.*

2. Secondary aims

2A. To determine and compare the effects of anamorelin vs placebo on serum procollagen 1 intact N-terminal (P1NP), a biochemical marker of bone formation. *Hypothesis: Anamorelin will increase P1NP.*

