2B. Determine whether changes in muscle mass and P1NP are predicted by sex, age, Health ABC-Physical Performance Battery (HACB-PPB) score, protein intake, or adherence to the intervention.

2C. Describe the safety and tolerability of anamorelin.

2D. Determine and compare the effects of anamorelin vs placebo on appendicular and total body lean mass assessed by DXA. *Hypothesis: Anamorelin will increase appendicular and total body lean mass.*

3. Exploratory aims

3A. To gain additional information on the effects of anamorelin, we will describe and compare the effects of anamorelin on muscle strength (isokinetic leg strength and handgrip) and muscle performance (HABC-PPB). *Hypothesis: Anamorelin will increase strength and performance.*

3B. To examine group changes in serum IGF-1, in the bone resorption marker, serum C-telopeptide (CTX), and in spine and hip bone mineral density (BMD). *Hypotheses: Anamorelin will increase serum IGF-1, serum CTX (as a result of coupling to the increase in P1NP), and BMD of the spine and hip.*

Data obtained from this pilot study are critical to determine the feasibility and guide the design of larger studies to evaluate ghrelin receptor agonists as potential therapies to mitigate the dual hazard of OS.

Endpoints:

Primary: muscle mass by D₃-creatine dilution

Secondary: P1NP, appendicular and total body lean mass by DXA

Exploratory: isokinetic leg strength, handgrip, HABC-PPB, IGF-1, CTX, spine and hip BMD

RESEARCH DESIGN

A. Study design

This is a double blinded, placebo controlled 2-armed parallel group trial testing the effect of anamorelin versus placebo on 12-month changes in muscle mass (primary) and the above described secondary and exploratory endpoints in community-dwelling older adults with OS. Up to 250 will sign the screening consent form in order to enroll 32 subjects and to have 24 completers. Subjects will be normal weight and overweight men and postmenopausal women age 50 years and older with OS.

B. Schedule of activities

Visit schedule	Enroll Day -3	0	2 mo	6 mo	Day 361	12 mo	Footnotes
Consent	X						^a By food frequency questionnaire
Medical history		X	X	X		X	^b Physical activity and SarQoL®
Weight		X	X	X		X	^c Isokinetic leg endurance on each visit and hand grip on 0, 2, 6, and 12 mo
Blood pressure		X		X		X	^d HACB-PPB at 0, 2, 6 &12 mo

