Secondary aims - With 4 measurements (baseline, 2, 6, and 12 months), we will test whether the change over time is linear with use of linear models with random effects. The observed pattern of change in ALM over time will give an indication of the potential long-term benefit (or lack thereof) of anamorelin treatment. A significance level of 0.05 will be used.

The findings from secondary (and exploratory) analyses will be used for hypothesis generation, rather than to draw conclusions.

Exploratory aims – Exploratory outcomes will be analyzed as described above. For those with more than two measurements, the pattern of change will be analyzed as described above for ALM.

The primary analyses will follow intention-to-treat principles. The intent to treat population will include all subjects who had 1 or more visits after visit 0 (baseline). We will also perform per protocol analyses, in which subjects who develop clinical conditions during the study that influence the study outcomes (i.e., started treatment on an osteoporosis drug or glucocorticoids) or with selected protocol deviations will be excluded. Data will be diagnosed to evaluate validity of model assumptions. Assumptions of normality and homoscedasticity will be evaluated in these models and appropriate variable transformations will be applied if needed to satisfy model assumptions. If model assumptions do not hold for the linear mixed models, robust standard errors will be used. An exploratory per-protocol analysis will also be performed.

Safety and tolerability measures will be summarized for each treatment group based on clinical symptoms and circulating levels of glucose and ALT/AST. Adherence will be assessed by intake diary and pill counts.

K. Withdrawal from the study

Participants can go permanently “off study” only for withdrawal of consent, defined as no longer wishing to participate in all aspects of the trial. The PI may also withdraw participants for safety reasons. Participants can be off of study pills (non-adherent) but remain in the study and return for scheduled follow-up visits. Participants who are instructed by their doctor to gain weight during the study will not be withdrawn from the study.

PROTECTION OF HUMAN SUBJECTS

a. Materials and potential risks

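### The robust-standard-error fallback for the mixed models names no small-sample correction or reference distribution, and its ordinary uncorrected form is anti-conservative with 24 to 32 subjects

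*Combined protocol and SAP*

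**What the plan says.** Section J (Data analysis) puts the four-visit secondary outcomes into mixed models: "we will test whether the change over time is linear with use of linear models with random effects". It adds "A significance level of 0.05 will be used", without saying whether tests are one- or two-sided. Exploratory outcomes with more than two measurements are handled the same way.

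Normality and homoscedasticity are then to be checked, and "appropriate variable transformations will be applied if needed to satisfy model assumptions". The next sentence is the fallback: "If model assumptions do not hold for the linear mixed models, robust standard errors will be used". Nothing further is said about the type of robust estimator, a small-sample correction, degrees of freedom or a reference distribution.

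Section A (Study design) fixes the size: "Up to 250 will sign the screening consent form in order to enroll 32 subjects and to have 24 completers". Allocation is one to one (Objectives and endpoints), so about 12 to 16 subjects per arm. The intention-to-treat set takes anyone with at least one post-baseline visit, so the number of independent subjects in a mixed model lies between 24 and 32 if recruitment and retention go as planned.

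Section J also says that secondary and exploratory findings serve to generate hypotheses and not to support conclusions. The primary analysis is a two-sample t-test, or ANCOVA if the groups are imbalanced.

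**The concern.** The sandwich variance estimator is justified when the number of independent subjects is large. With about 12 per arm, the uncorrected form is biased downward, because residuals around fitted means are too small. Referring the statistic to a normal distribution also ignores the uncertainty in the variance estimate. Both effects shorten intervals and raise the type I error.

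The outcomes concerned are P1NP, which section I treats as the leading secondary outcome and gives its own power calculation, appendicular and total lean mass, and the exploratory outcomes measured repeatedly. The trial is a pilot meant to inform larger studies, and section J intends to read long-term benefit from the pattern of change in appendicular lean mass. Intervals that are too short would mislead that planning even without a formal claim.

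Because the sentence is open, the choice between variants with different error rates could be made after the data are seen. Section G (Randomization) lists the study statistician among those not blinded to assignment, which is a further reason to settle it now.

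**Working it through.** **Inputs from the protocol.** Nominal level 0.05 (two-sided assumed); 32 enrolled and 24 completers, 1:1, so n = 12 or 16 per arm; visits at 0, 2, 6 and 12 months; P1NP SD of change 0.267 nmol/L, difference 0.32 nmol/L, stated power 82% with 12 per group. The protocol gives no within-subject covariance, skewness or variance ratio, so those are assumptions in the simulations below.

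**1. The plan's own figure.** Standard error = 0.267 × √(2/12) = 0.109; 0.32/0.109 = 2.936. The normal approximation gives power Φ(2.936 − 1.960) = 83.5%; the noncentral t on 22 df gives 80.1%. The stated 82% lies between them, so it is reproduced. The plan states no error rate for the fallback other than the nominal 5%.

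**2. Closed form, one-df arm contrast, normal and complete data.** The uncorrected sandwich (CR0) variance is (n − 1)/n times the unbiased one. The true error is P(|t| > c × √((n − 1)/n)) on 2n − 2 df, where c is the critical value used.

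- n = 12, normal reference: 1.960 × √(11/12) = 1.877; P(|t22| > 1.877) = **7.4%**.
- n = 16, normal reference: 1.960 × √(15/16) = 1.898; P(|t30| > 1.898) = **6.7%**.
- n = 12, t reference: 2.074 × 0.957 = 1.986; **6.0%**.
- n = 16, t reference: 2.042 × 0.968 = 1.977; **5.7%**.

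Against the correct t interval, the half-width with a normal reference is 1.877/2.074 = 0.905 (about 10% too short) at n = 12 and 1.898/2.042 = 0.929 (about 7% too short) at n = 16.

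**3. Skewed or unequal-variance data.** Per-subject contrasts, 200,000 runs per setting, balanced arms, exponential errors and/or an SD ratio of 2:

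| Method | 24 subjects | 32 subjects |
|---|---|---|
| CR0, normal reference | 6.9 to 9.3% | 6.4 to 8.4% |
| CR0, t(N − 2) | 5.4 to 7.8% | 5.3 to 7.3% |
| CR2, t(N − 2) | 4.4 to 6.8% | 4.6 to 6.5% |

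The upper ends all come from skew combined with an SD ratio of 2. In that setting with arms of 10 and 14, CR0 with a normal reference reaches 11.1%.

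**4. Four-visit model, one-df tests.** Random intercept and slope, 4,000 runs per setting, working covariance held fixed:

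| Method | 24 subjects | 32 subjects |
|---|---|---|
| CR0, normal reference | 7.0 to 8.4% | 6.4 to 7.8% |
| CR1, t(N − 2) | 5.2 to 6.2% | 5.0 to 6.4% |
| CR2-type, t(N − 2) | 4.9 to 5.6% | 4.7 to 5.7% |
| CR3-type (Mancl-DeRouen kind), t(N − 2) | 3.9 to 4.7% | 4.1 to 4.9% |

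A separate simulation with partial follow-up, skewed outcomes and optional covariates (12 settings, 3,000 trials each) gave 6.5 to 8.8% for CR0 with a normal reference and 3.5 to 4.9% for Mancl-DeRouen with t.

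**5. Multi-df tests.** CR0 with a chi-square reference gave 9.9 to 13.9% for a 3-df group-by-visit test and 13.6 to 18.2% for a 4-df test of departure from linearity (two df per arm). For the 4-df test, correction with N − 2 denominator df is not enough: in two 32-subject unequal-variance settings CR2-type gave 8.4% and 9.8%, and CR3-type 7.0% and 8.3%.

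**The case against.** The strongest reply is that the protocol does not prescribe an uncorrected sandwich or a normal reference. A statistician could apply the same sentence with a corrected estimator and t, and a one-df test would then run close to 5%. That stands. The inflation belongs to a common implementation that the sentence permits, not to the plan as written.

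A reader might infer that the secondary tests will simply run at 6.5 to 9%. The documents do not support this. The fallback is conditional, transformations are also provided for, and the mixed-model test that section J describes is one of linearity, not a month-12 arm contrast. Nor does the protocol say that the fallback governs the two-group P1NP comparison for which power was computed.

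A reader might also infer that the fallback does harm. That too goes too far, because the right comparator is keeping model-based errors after the assumptions have failed. In a simulation with 12 per arm, a random-intercept working model and true slope variation added (assumed slope SD 0.5 to 1.5 times the intercept SD, 20,000 runs), model-based tests ran at 7.8 to 16.6%, the uncorrected sandwich at 7.1 to 7.5% with a normal reference, and at 5.7 to 6.1% with t(22). There the fallback helps; it is just not as good as it could be.

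Finally, the primary t-test is untouched and the affected analyses are declared hypothesis-generating. Both points are true and limit the consequence. They do not remove it, since interval width still feeds the design of the next trial.

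**Conclusion.** The point holds as an under-specified fallback whose ordinary reading is anti-conservative at this sample size. If the fallback is reached and an uncorrected sandwich is used, a nominal 5% one-df arm contrast runs at about 7.4% (24 subjects) or 6.7% (32) with a normal reference, and up to about 9% with skewed or unequal-variance data in balanced arms. With a t reference it runs at about 6% under normal data. Multi-df tests can be clearly worse.

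The closed-form figures need only a two-sided level, balanced arms, complete data and normality. The other ranges depend on assumed covariances, error shapes and variance ratios, and the four-visit results on a fixed working covariance. The primary analysis is unaffected. Importance is modest: a cheap improvement worth making before the data are analysed.

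**What to change.** Replace the fallback sentence in section J with wording such as:

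> Should the mixed-model assumptions still fail after transformation, inference will use cluster-robust standard errors with a small-sample correction (Mancl-DeRouen, or CR2 with Satterthwaite degrees of freedom) and t or F reference distributions.

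For a multi-df test of linearity or of group by visit, also name the small-sample denominator degrees of freedom, because N − 2 left the 4-df test at 7.0 to 9.8% in the settings above. State which of the two estimators will be used, so that the choice is not left open.

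The cost is one sentence. Intervals become slightly wider, and Mancl-DeRouen is mildly conservative (one-df tests at 3.5 to 4.9%). CR2 is closer to nominal in the four-visit model but still ran at 6.5 to 6.8% with strong skew and an SD ratio of 2; that was with t on N − 2 df, and the Satterthwaite version was not simulated. Naming Kenward-Roger degrees of freedom for the model-based analysis would be optional; nothing here shows that it is needed.

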ECGs before and 1 & 4 hr post dose		X					^e DXA total body scans at 2, 6, &12 mo; spine and non-dominant hip scans at 12 mo (screening scans will serve as baseline)
Diet assessment ^a		X				X	^f Serum P1NP at 0, 2, 6, and 12 mo; serum IGF-1 and CTX at 0 and 12 mo; serum 25(OH)D at 0 and mo 6; and alpha-acid glycoprotein at visit 0; archive 4 aliquots serum and 1 of plasma at 0 and 12 mo.
Questionnaires ^b		X		X		X	^g Safety monitoring: fasting plasma glucose & serum AST/ALT at 0, 2, 6, and 12 mo; symptoms and other AEs documented
Muscle strength ^c	X	X	X	X		X	^h By pill diary and counting returned pills
Muscle perform. ^d		X	X	X		X	ⁱ Administer 60-mg oral dose of D ₃ -creatine
DXA scans ^e			X	X		X	^j Collect fasting spot urine for D ₃ -creatine dilution determination
Study blood ^f		X	X	X		X	
Dispense pills		X	X	X			
Safety measures ^g		X	X	X		X	
Adherence ^h			X	X		X	
D ₃ -creatine dosing ⁱ	X				X		
Fasting spot urine ^j		X				X	
Waist circumference						X	

In addition to the above study visits, we will contact participants by telephone at 4, 8, and 10 months to determine whether they have any study related concerns and to remind them of the importance of taking one study pill per day. The content of these calls will be documented on the Call/comment Log.

C. Inclusion and exclusion criteria

Inclusion criteria: Ability to sign informed consent form; community dwelling men (who are sterile or agree to use contraception throughout the study) and postmenopausal women (no menses for 5 years; early postmenopausal women are ineligible because their bone turnover rate is changing rapidly); age 50 years and older; sarcopenia defined as maximum grip strength <35.5 kg (men) and <20 kg (women) in either hand (excluding hands with severe pain or recent surgery) and/or gait speed <0.8 m/sec (11); osteopenia defined as spine (at L1, L2, L3, or L4) or non-dominant total hip or femoral neck BMD T-score between -1.0 and -2.5; mini-mental state examination (MMSE) score >21.

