DXA scans Radiation exposure to the region of interest from the 8 screening and intra-study DXA scans (2 spine, 2 hip, and 4 total body scans) is 60 microsieverts. This amount of radiation is about the same as one receives normally in 6 days from natural background sources.

Muscle strength and physical function testing Risk of injury from testing of physical capacity is very low. A potential risk is the risk of losing balance during the HABC-PPB testing. However, the examiner will remain on hand to help volunteers who are unsteady. At the end of the strength testing, volunteers may experience muscle tightness, soreness, cramping, or strain, but these symptoms are rare and transient.

b. Adequacy of protection against risks

Informed consent

Informed consent for both the screening and the study will be obtained from each participant by the PI or registered nurses on the Metabolic Research Unit. It will be obtained at the beginning of the screening and enrollment visits. The consenting process will take place in a private area. The PI or one of the registered nurses on the research team will go over the study information and will obtain the participants' consent. The full nature of the study (purpose, procedures, risk) will be provided to participants. Participants will be encouraged to ask questions and will be told that they can cease participating in the study at any time for any reason. Participants' consent will be documented in written form, signed by the participant and by the PI or her designee. The study protocol and consent form will have been approved by the Tufts Institutional Review Board (IRB). All personnel coming in contact with the participant will be trained and certified by the Tufts IRB in the ethical conduct of research. Subjects must be able to read and, in the view of study staff, indicate understanding of the study purpose and procedures to be eligible.

Protection against risks

To optimize intra-study safety and tolerability, we will take the following steps:

We will strictly adhere to protocol inclusion and exclusion criteria.

Blood sampling will be done by experienced nurses on the Metabolic Unit. They will use aseptic techniques.

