DXA scans will be performed by DXA technicians who are experienced and certified by International Society for Clinical Densitometry and the State of MA. Should a participant's BMD of the spine or hip decline by >7% on 2 consecutive measurements, the participant will be notified and referred to his/her PCP. The participant will remain in the study.

The muscle performance measurements will be administered by an experienced research coordinator who will observe the subject during testing.

Because of the potential of anamorelin to increase fasting plasma glucose, we will monitor glucose on each visit. If it is elevated (≥ 200 mg/dl), we will repeat the measurement. If again elevated ≥ 200 mg/dl, the study pills will be discontinued. Discontinuation of study pills will be managed without unblinding the study team, and those participants will continue with study measurements (for the intent-to-treat analysis). Subjects will be asked to consume their usual dinner on the evening prior to each study visit.

Sporadic, mild increases in serum AST/ALT have been observed in subjects on anamorelin. We will monitor AST/ALT on each study visit and discontinue use of anamorelin if these levels exceed 2x the upper end of the reference range (>74 and >68 MU/ml, respectively) on repeat measurement.

In order for participants to achieve therapeutic levels of anamorelin, we will exclude subjects on CYP3A4 inducers which may increase the metabolism of anamorelin (e.g., rifampin). We will also have participants take study pills 1 hour before breakfast, as food reduces anamorelin bioavailability.

To minimize risk that anamorelin levels become supra-therapeutic, we will: a) instruct participants never to take more than one study pill per day (that is, not to 'catch up' after missing a dose); b) exclude participants taking strong CYP3A4 inhibitors (ketoconazole, clarithromycin, itraconazole, nefazodone, telithromycin); c) exclude participants taking drugs with high binding affinity to AAG because they have the potential to displace anamorelin from binding (e.g., carvedilol, chlorpromazine); d) exclude participants taking inhibitors of P-glycoprotein (e.g., verapamil, quinidine), and e) inhibitors of OATP1B3 (e.g., cyclosporine, rifampicin)

We will instruct participants to notify [name] of any new prescriptions (before taking the first dose) and of any changes in health status or of any hospitalizations or emergency room visits.

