Nonclinical data indicate that the T_{max} in cardiac tissue is delayed compared with plasma T_{max} (4 hrs vs 1 hr, respectively). We will perform a screening ECG and exclude individuals with clinically meaningful abnormalities. We will also perform ECGs before and 1 and 4 hrs after the first dose of the study pills.

Stopping rules

- We will discontinue the subject's participation in the study if the QT interval exceeds 470 ms or if other clinically meaningful ECG changes occur at either 1 hr or 4-hrs post first dose (4 hrs post dose is the time when the anamorelin concentration in cardiac tissue is maximal).
- We will discontinue the subject's participation in the study in the event that he/she develops cardiac symptoms (e.g., chest pain, chest pressure, palpitations) or evidence of significant fluid retention (peripheral edema, pulmonary congestion).
- We will discontinue a subject's participation in the study if he/she is prescribed the following drugs during the study:
 - CYP3A4 inhibitor (ketoconazole, clarithromycin, itraconazole, nefazodone, or telithromycin)
 - Channel blocking antiarrhythmic medication (flecainide, procainamide, propafenone, quinidine)
 - Drugs with high affinity to AAG (carvedilol, chlorpromazine)
 - Inhibitors of P-glycoprotein (verapamil, quinidine)
 - Inhibitors of OATP1B3 (cyclosporine, rifampicin)
- We will discontinue a subject's participation in the study if he/she develops glycemia defined as fasting plasma glucose ≥ 200 mg/dl on two consecutive measures.

Subjects developing these findings or symptoms will be referred to their physicians and these adverse events will be recorded and reported to the IRB, the NIH, and Helsinn Therapeutics. The study physician will follow up with the subject and his/her physician until symptoms have been appropriately addressed.

We will exclude subjects with eGFR < 30 ml/min.

The study will be approved by the Tufts IRB before anyone will be recruited for the study. All study personnel have been certified by the Tufts IRB to work with clinical research participants. All research activity will take place at the HNRCA. Written informed consent will be obtained from each participant.

The PI will inform the IRB of any updated information that may affect the conduct of this study or subject safety, rights, welfare or willingness to take part in the research.

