The FDA will be kept informed of the most current IRB approved protocol throughout this study so that the IND can be updated. We will send annual reports to the FDA that are linked in timing and content to the Continuing Review information sent annually to the IRB. We will send a summary of the study results to the FDA at the end of the study.

Record retention - Subjects' records will be retained for the timeframe described in the record retention policy of the "[SOP – Records Retention Timeframe – Investigators.](#)"

Vulnerable Populations: This study does not include vulnerable populations.

Alternatives - Subjects may choose not to participate in the study. Their participation is voluntary. Everything done in this study is being done for research.

Withdrawal - Subjects are free to stop their participation at any time for any reason. Participants will be considered lost to follow-up if we are unable to reach them by telephone or email after trying weekly for 10 weeks. At that point, no further attempts will be made to contact them. Should subjects decide to withdraw from the study, the study measurements made before their withdrawal may be included in the scientific analysis and publication of the study results. To withdraw from the study, subjects can contact [name] at [contact]. [name] may also end a subject's participation in the study at any time in order to protect his/her safety or to maintain the smooth conduct of the study.

c. Potential benefits to subjects

This study is not designed to benefit individual subjects. Screening lab results will be made available to the subjects. Subjects will have the option to receive copies of their screening spine and hip DXA scans two to three weeks after their visit. Intra-study laboratory tests will be made for research only and will not be shared with participants. If any adverse medical conditions are discovered during the study, subjects will be notified and referred to their doctor.

Risk/benefit assessment

The risks incurred are minimal relative to the potential benefit of gaining information about one's health.

Payment plan

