Subjects will be paid \$25 for the screening visit. Each subject who completes the study will be paid an additional \$700 for transportation and miscellaneous expenses. Of this, \$200 will be given after the baseline visits, \$100 will be given after the 2-month and the 6-month visits, and \$300 will be given after the 12-month visits. Participants asked to return for safety laboratory assessment will receive \$25 for each extra visit. If a subject needs to remain in the study for up to 10 extra days for any reason (such as snow days, unrelated minor illness, unanticipated schedule change), he/she will continue in the study, however the stipend will not be increased. If a subject drops out of the study or is obliged to skip any of the visits, his/her payment will be pro-rated to the portion of the protocol that he/she completed according to the payment schedule described above. The HNRCA will mail a check to participants about two to three weeks after the visits described above.

Reimbursement for research related injury

Emergency medical treatment will be given to a subject who is hurt or gets sick as a direct result of being in this study. The subject or his/her insurance carrier will be required to pay for any such medical care. There is no money to pay for treatment if a subject gets hurt or sick as part of this study. Any needed medical care is

available at the usual cost. All needed facilities, emergency treatment, and professional services are available to the subjects, just as they are to the general public. The institution will not pay for treatment if a subject becomes ill or injured as part of this study.

Collection and storage of human biological specimens

Upon completion of the study and data analysis, any remaining blood samples will be discarded. In addition to testing during the study, blood and urine will be archived for future measurements (i.e., batched measurements at the end of all subject visits). All samples will be used for the purpose of this study only and will be discarded at the end of the study. Participants will be issued an individually identifiable number linking records, specimens and data. Urine samples will be de-identified before they are sent to [name] at UC Berkeley for D₃-creatine analysis.

Vulnerable populations – This study does not include vulnerable populations.

ClinicalTrials.gov – This study will be registered in ClinicalTrials.gov at least 21 days before the first subject is enrolled.

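### The BMD referral rule needs a fall of more than 7% on two consecutive measurements, but only one follow-up spine and hip scan is scheduled

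*Combined protocol and SAP*

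**What the plan says.** The section on protection against risks sets one rule specific to bone density. Should a participant's "BMD of the spine or hip decline by >7% on 2 consecutive measurements", the participant is told, is referred to their primary care physician and stays in the study.

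Footnote e of the table in section B (Schedule of activities) gives the scan times: total body at 2, 6 and 12 months, and "spine and non-dominant hip scans at 12 mo (screening scans will serve as baseline". The DXA paragraph under known potential risks counts 8 scans per participant, "2 spine, 2 hip, and 4 total body scans", with a dose of 60 microsieverts.

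Two other safety rules in the same section use confirmation. For a raised glucose, "we will repeat the measurement"; the Stopping rules express the same criterion as at least 200 "mg/dl on two consecutive measures". For AST/ALT, the level must exceed the limit again on a repeat test. The BMD rule mentions no repeat.

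Section c (Potential benefits to subjects) adds a general provision: "If any adverse medical conditions are discovered during the study, subjects will be notified and referred to their doctor".

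**The concern.** A decline is measured against the screening scan. With one later scan there is one decline to assess, and a rule that requires it on two measurements in a row has nothing to work with. The statement that the participant stays in the study also suits a rule that can trigger partway through, not one that can first be assessed at the last visit.

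At stake is a safeguard the sponsor chose to include. Participants enter with osteopenia, and the Background says the drug's effect on bone parameters has not been reported. As written, someone whose 12-month scan shows a fall of more than 7% does not meet the only BMD-specific rule. Staff would have to fall back on the general clause, which sets no BMD threshold, or arrange a scan the protocol does not mention. The participant may not otherwise learn of the fall, because the scan copies on offer are those from screening: "Subjects will have the option to receive copies of their screening spine and hip DXA scans".

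**Working it through.** **Scan count.** The inputs are the screening visit description (section D), footnote e (section B) and the DXA paragraph under known potential risks.

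- Total body: screening, 2, 6 and 12 months = 4
- Spine: screening and 12 months = 2
- Hip: screening and 12 months = 2
- Total: 4 + 2 + 2 = 8, which reproduces the protocol's figure.

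Follow-up scans per BMD site = 2 − 1 = 1. The rule needs 2, so the shortfall is 1 and the number of consecutive follow-up pairs is 0.

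The opening visit summary says the 2- and 6-month visits repeat the baseline measures, which might suggest further spine and hip scans. Footnote e and the count of two per site rule that out.

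**Is one scan enough to act on?** The DXA paragraph of section F gives precision of 1.25% (spine), 1.60% (total hip) and 1.94% (femoral neck). Take scan error as normal and as the only variation around a common true change. Then:

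- SD of a measured change = √2 × precision
- 95% least significant change = 1.96 × SD
- Chance of a measured fall above 7% with no true change = 1 − Φ(7 / SD)
- The same chance with a true loss of 2% = 1 − Φ((7 − 2) / SD)

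The 2% is the top of the range of about 1–2% per year in the Background.

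| Site | SD of change | Least significant change | Fall >7%, no true change | Fall >7%, true loss 2% |
|---|---|---|---|---|
| Spine | 1.77% | 3.46% | 0.004% | 0.23% |
| Total hip | 2.26% | 4.43% | 0.10% | 1.36% |
| Femoral neck | 2.74% | 5.38% | 0.54% | 3.42% |

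The 7% threshold exceeds the least significant change at every site, so a one-scan rule would raise few false alarms.

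**Participants affected.** With 24 completers and a true 2% loss in everyone, the site with the largest figure (femoral neck) gives 24 × 0.0342 = 0.82 expected. This is not an upper bound. If true change also varied between people with an SD of 1% to 2% (an assumption; the protocol gives no figure), the SD of a measured change becomes √(2.74² + 1²) = 2.92% to √(2.74² + 2²) = 3.39%, and the expected number becomes about 1.0 to 1.7.

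**The case against.** The strongest counter-argument is that the sentence can be read so that it works.

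- **A fall between two consecutive scans.** On a loose reading, screening and 12 months are the two measurements, and the schedule supplies that pair. But the sentence asks for the decline to appear on two measurements, and the glucose stopping rule uses nearly the same phrase to mean two abnormal results. If the loose reading was intended, the sentence still needs rewording.
- **An implied confirmatory repeat.** For glucose, two consecutive measures does mean a test and its repeat, so the same could be meant for BMD. The AST/ALT wording is also brief: it requires a repeat but does not say when. Even so, both laboratory rules mention a repeat and the BMD rule does not, and the scan count and dose allow for none. The Payment plan names extra visits for laboratory work only ("Participants asked to return for safety laboratory assessment will receive"). That is weak evidence, since a payment clause does not list every permitted visit, and the same section lets a participant stay up to 10 extra days.
- **Remaining in the study.** This may only mean that bone loss is not a reason for withdrawal. That is fair, so the sentence supports the point but does not settle it.
- **The general clause.** It leads to the same action and could cover a large 12-month fall. It stands as a partial backstop, but it leaves staff to decide what size of fall counts as an adverse medical condition.

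The small size of the issue is not in dispute.

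**Conclusion.** The concern holds. On its plain wording, the rule cannot be met from the scheduled scans: two follow-up measurements per site are needed and one is planned, for every participant. An unscheduled repeat could satisfy it, but none is written. This conclusion rests on the schedule alone; the scan-error calculations bear only on the choice of remedy and the likely number affected.

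It is a minor safety-monitoring error that should be corrected. Few participants are likely to be involved: about 0.8 of 24 completers at the femoral neck if everyone truly loses 2% and scan error is the only other variation, and somewhat more if true losses vary between people.

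**What to change.** Reword the rule so that notification and referral follow a spine or hip BMD decline of more than 7% from screening at the 12-month scan. Drop or adapt the statement about remaining in the study, since this is the final visit. This costs one sentence and no added scans.

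If the sponsor wants confirmation, state that a repeat spine or hip scan will be done after such a fall at 12 months, as is already done for the laboratory rules. That adds a scan only for flagged participants and requires an update to the 8-scan, 60-microsievert statement.
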